9.2.3 Suspected unexpected serious adverse reactions (SUSARs)

As no investigational medicinal product is used this chapter is not applicable.

9.3 Annual safety report

As no investigational medicinal product is used this chapter is not applicable.

9.4 Follow-up of adverse events

All AEs will be followed until they have abated, or until a stable situation has been reached. Depending on the event, follow up may require additional tests or medical procedures as indicated, and/or referral to the general physician or a medical specialist.

SAEs need to be reported till end of study within the Netherlands, as defined in the protocol

As this study comprises a clinical studies in non-critical indications where patients are treated for a relatively short time and the drugs/procedures under investigation are well characterised and known for not harming patients, no DSMB is needed according to the EMEA guidelines [67]. Furthermore, the risk attached to the investigation is considered negligible (see §13: STRUCTURED RISK ANALYSIS, p78).

A Safety Committee however will be established to perform interim analyses on the safety data. This committee is an independent committee and consists of:

- a statistician (Dr. [name]).
- a surgeon (Dr. [name]),
- an interventional radiologist (Prof. dr. [name])

The Safety Committee will meet at least yearly during the course of the study, and will consider results of data-monitoring:

- recruitment figures and losses to follow-up presence and completion of research file
- informed consent (1-10%)
- adherence to in- and exclusion criteria (first 3 participants per centre, than 1-10%)
- Source Data Validation: 1-10% based on predefined variables including primary end-point, clearly related to safety and validity of the project
- missed (1-10%) and reported (S)AEs
- validation of which instructions are given to patients
- validation of availability of study procedures including SOPs
- verification of collection, labelling and storage of biological samples
- suggestion of additional data analyses
- Advise on protocol modifications suggested by investigators or sponsors (eg to inclusion criteria, trial endpoints, or sample size)
- Monitor planned sample size assumptions
- Monitor continuing appropriateness of patient information
- Monitor compliance with previous Safety Committee recommendations
- Considering the ethical implications of any recommendations made by the Safety Committee

Furthermore they will perform an independent interim-analysis (§8.7, p58) and a safety endof-study analysis (§8.4.1, p56). This report will be sent to the Study Coordinator, who will send this report to the CCMO including the planned action.

A more detailed description of the expected role and responsibilities of this Safety Committee is described in the charter.

Addendum 20-02-2019:

An interim analysis was performed on 17-04-2018. Results were reported to the Safety Committee, who approved continuation of the trial according to protocol (v1.4 at the time) with no adjustments.

EfFECTS

10. STATISTICAL ANALYSIS

10.1 General remarks

All (statistical and economical) analyses will be supported by epidemiologists and biostatisticians from the LUMC.

All continuous data (e.g. age, FDG-PET/CT standardised uptake level (SUV), volumes of care, hospitalisation and sick leave days, Tg-level, questionnaire scores, etc.) will be assessed for (log)normality.

All categorical data (e.g. sex, FDG-PET/CT positive or negative, malignant or benign, histology, etc.) are treated as either ordinal or nominal.

One year is defined as 365.242199 days. Age, overall survival, disease-free-survival are computed with respect to the date of the (last) US guided FNAC that led to study enrolment. Survival is computed, using the Kaplan-Meier method, taking into account censored data (censored to the date of last follow-up or death (for all but overall survival)). For comparison of Kaplan-Meier estimates, the logrank statistic will be used (as the Breslow and Tarone-Ware tests are better used when the data does not fulfil the proportional hazards assumption; they are both weighted versions of the logrank test giving extra weight to events happening earlier on. The Tarone-Ware has slightly less extreme weightings. Both should be avoided in case of a high level of censoring or unequal censoring between groups).

All prices will be calculated based on national price levels (in Euro, €), indexed to the year of first patient inclusion (2015). Price-index-numbers will be used to account for price changes during the years of patient inclusion and follow-up. In case of costs distributed over several years, net present values are computed using a constant 4% discount rate and effects using a constant 1.5% discount rate, which is a common method in the Netherlands (other countries usually use uniform discounting). For all computations, the methods for cost-research of Hakkaart-vanRoijen et al.[68] will be used.

Missing values will not be completed by any means (e.g. average). In case of missing values, the fraction missing values will be stated. Multivariate analysis might therefore only be performed on a subset of patients (without missing values in all independent parameters), however due to the nature of the important independent parameters, we expect that this "subset" of patients will be over 95% of the study population.

All data will be presented quantitatively. All analysis will be performed according to the intention to treat. In case of study-arm cross-over (e.g. a PET-negative patient in the experimental studyarm who is operated upon due to high clinical suspicion of missed malignancy), this will be described.

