2.2 Secondary Objectives

2.2.1 Secondary Objective 1: Treatment Outcome

- SO1a: To determine the difference in unbeneficial treatment between FDG-PET/CT driven and routine surgery in this population including thyroid lesions of all sizes (i.e. both ≤10 mm and >10mm).
- SO1b: To determine the effect of incorporation of FDG-PET/CT on the complication-ratio.
- SO1c: To determine the false-negative rate of FDG-PET/CT in this population (i.e. in how many patients with malignancy will watchful-waiting be performed) based on both 12-month and (retrospective) 5-year follow-up.
- SO1d: To determine the influence of lesion size, pathological classification and patient characteristics on the diagnostic accuracy (subgroup analysis) of FDG-PET/CT.
- SO1e: To determine whether incorporation of FDG-PET/CT of the head and neck leads to overdiagnosis in non-thyroidal incidental findings (whole-group analysis).
- SO1f: To determine the short-term overall and disease free survival in both study arms.
- SO1g: To determine which factors hamper implementation of this modality for this indication (structured interviews).
- SO1h: To determine the fraction of patients that cannot be reassured by a negative PETscan (experimental arm only) despite careful selection of patients (implementability).

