3. STUDY DESIGN

A partially-blinded, prospective, multi-centre, block-randomised controlled trial (RCT) is designed. After obtaining written informed consent, patients are registered centrally, FNAC is reviewed centrally and thereafter patients are randomised to either the experimental study-arm (arm A: FDG-PET/CT driven management decisions) or a control study-arm (arm B: surgery regardless FDG-PET/CT result) using a 2:1 allocation ratio. The latter is performed both for methodological purposes (the treatment of the subjects in the control study arm is well investigated and described before) and to satisfy the assumption that patient prefer the experimental study-arm. The result of randomization is blinded to the treating physicians and central FDG-PET/CT review committee. Allocation is adaptively stratified using the minimisation method on the centre of inclusion and the most prognostic features of DTC known at this stage of patient work-up: (US) lesion size (0-10 mm/11-20 mm/21-40 mm/40+ mm), patient sex, patient age (<45yr, \geq 45yr) and Bethesda classification according to central review committee (atypia of unknown significance/follicular lesion of unknown significance (III) or (suspicion) for a follicular neoplasia (IV)).

Based on the study arm allocation and PET result, treating physicians will either be told to cancel scheduled diagnostic thyroid surgery (allocation to the experimental arm with a negative FDG-PET/CT at central review or ~32/132 patients) or to proceed with surgery (all other cases or 100/132 patients). In case surgery is cancelled the patients need to be followed-up by watchful waiting and a confirmatory ultrasonography (including FNAC) after 12 months. Patient allocation will not be disclosed to prevent study withdrawal, however in case surgery is cancelled unblinding is unavoidable (~25% of all included patients).

The Gold Standard is histology, revised by a (central) dedicated pathologist panel, obtained from surgery or 12-months follow-up, including US (+FNAC). All patients will be followed for at least 12 months after FDG-PET/CT to ensure all direct costs and complications are noted. Five years after inclusion of the last patient, long-term follow-up will be determined based on patient file review and contact with the general practitioner (flowchart Figure 1, p34 and

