8.3.4 Cytology and histopathology analysis

In the study, cytopathology and histopathology specimens are collected. After cytopathology is collected from individual patients during FNA (prior to study inclusion), cytopathology slides are reviewed at the Radboudumc by two experienced thyroid pathologists to ensure appropriate inclusion in the study. If the first and second pathologist disagree, a third dedicated pathologist will be consulted. Consensus upon classification as either Bethesda category III or IV has to be reached before inclusion of a patient into the study (§8.2.1, p46). Cytopathology samples are returned and stored in local tissue banks at the centre where the FNA was initially performed. Before start of the study, a consensus meeting was held with the dedicated pathologists from the different centres to minimise interobserver variation.

After surgery, thyroidectomy specimens are being stored at the hospital where the surgery has been performed and will be collected at the end of the study. After surgery in all appropriate study patients is completed, histopathology specimens will be reviewed at the Radboudumc by the same experienced thyroid pathologists but an expert of the LUMC may be consulted for specific cases. Characteristics of the lesion like type of lesion, size, cell type, inflammation and vascularity will be scored (see §8.1.2, p45) in adherence to the World Health Organization guidelines [64].

Next, cytological and histopathological tissue characteristics will be analysed in relation to FDG-PET/CT findings in order to determine whether specific tissue characteristics can explain false positive or negative FDG-PET/CT results - like for instance high vascularity or cell type.

Definition of malignant and benign thyroid nodules:

A nodule is considered malignant, in case malignancy is diagnosed at the location of the nodule. All other cases are considered benign nodules.

[figure not shown]
Following advanced insights and in accordance with WHO guidelines, pre-malignant entities such as non-invasive follicular thyroid neoplasm with papillary-like nuclear features (NIFTP), follicular tumor of uncertain malignant potential (FT-UMP) and well-differentiated tumor of uncertain malignant potential (WDT-UMP) are distinguished. These are strictly considered benign though potentially precancerous lesions, for which thyroid lobectomy is justified [65, 66].

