13.1.2 Possible delay of treatment for DTC

a. Level of knowledge about mechanism of action

In contrast to the other head and neck tumours, cervical lymph node metastases are only of limited (or no) prognostic value in multivariate analysis of PTC patients. In FTC the prognostic value is not very clear, but seems to be of at least some prognostic significance. The possibility for a locoregional recurrence increases when cervical lymph nodes are present [76], but this rarely is the cause of death in patients with DTC.

There seems to be some relation between DTC tumour size (T-stage) on 10-year disease-free and overall survival (T_{1-4} : 85%, 73%, 60%, 56% (for 10y DFS) and 100%, 93%, 87%, 72% (for 10y OS), respectively [77]). However after correction for age, vascular invasion, extracapsular invasion and MACIS score, only TNM stage remained.

The consequences of delayed treatment for DTC are considered to be minimal, due to the relative indolent growth of this disease and the limited influence on survival of transition from localised (stage I) to regional (stage II) disease (both 5-year overall survival 100%), all with good (curative) treatment options Appendix V: American Joint Committee on Cancer (AJCC) TNM classification of differentiated thyroid cancer, 7th edition, (§15.5 p94). [1]

b. Previous exposure of human beings with the test product(s) and/or products with a similar biological mechanism

Since the clinical implementation of fine needle aspiration cytology (FNAC) to diagnose thyroid carcinoma, few patients remain misdiagnosed as the false-negative rate of FNAC for malignancy in thyroid nodules is less than 5% (Appendix IV: Performance of FDG-PET/CT in indeterminate thyroid nodules, §15.4, p92). An observational retrospective study comparing 12 cases with DTC and benign/non-diagnostic FNAC with 39 controls with DTC and

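### Section 10.1 censors deaths in disease-free survival, so SO1f as written estimates time to a disease event and not disease-free survival

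*Protocol*

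**What the plan says.** Section 10.1 names the estimator, "Survival is computed, using the Kaplan-Meier method, taking into account censored data", and the test between arms: "For comparison of Kaplan-Meier estimates, the logrank statistic will be used". Its censoring rule is "censored to the date of last follow-up or death (for all but overall survival". Death is therefore an event for overall survival and a censoring time for anything else.

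The same section fixes the time origin: "Age, overall survival, disease-free-survival are computed with respect to the date of the (last) US guided FNAC that led to study enrolment".

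Disease-free survival enters through SO1f in section 2.2.1: "To determine the short-term overall and disease free survival in both study arms". Section 8.1.2 lists it beside overall survival, to be determined once study-related follow-up of the last patient is complete. Section 10.4 names both as possible outcomes for multivariate models. None of these places says which occurrences are disease-free survival events, and none counts death as one.

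On the order of FNAC and randomisation, section 8.3.4 has "After cytopathology is collected from individual patients during FNA (prior to study inclusion", and section 3 says that "patients are registered centrally, FNAC is reviewed centrally and thereafter patients are randomised to either the experimental study-arm".

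**The concern.** Disease-free survival is normally read as the probability of being alive and free of disease. Under the stated rule a patient who dies without an earlier recorded disease event leaves the risk set as a non-event, and Kaplan-Meier treats that patient as having the same future disease risk as those still followed. A reader of the published curve would take it to include deaths, and it would not. The label matters here because section 13.1.2 treats delayed treatment of thyroid carcinoma as a principal risk of the experimental strategy, and surgery is the main intervention it aims to avoid. A death from either cause belongs in an endpoint with this name.

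A smaller point concerns the clock. It starts before randomisation, in an interval that every randomised patient must have survived.

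**Working it through.** The protocol gives no expected event count, power or estimate for disease-free survival, so there is no figure of its own to reproduce. The check is a reading of the definitions, followed by illustrations of size.

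**1. Which endpoints the rule reaches.** The survival endpoints in use are overall and disease-free survival (sections 2.2.1, 8.1.2, 10.1, 10.4). Progression-free survival appears only in the abbreviation list. Exempting overall survival alone leaves disease-free survival under the rule that censors at death.

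**2. What is then estimated.** With constant disease hazard hd and death hazard hm:
- death censored: S(t) = exp(−hd·t), in which hm does not appear;
- death counted: S(t) = exp(−(hd + hm)·t).

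The first is the net disease-event curve. Only the second is disease-free survival.

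**3. Weight of one death.** Arm sizes are 88 and 44 (section 4.4). With everyone still at risk, one uncounted death is 1/88 = 1.1 points in arm A or 1/44 = 2.3 points in arm B.

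**4. Illustration at 12 months.** All rates are assumptions. Take hd = 0.013 per year and hm = 0.005 to 0.02 per year.

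| hm | death censored | death counted | difference |
|---|---|---|---|
| 0.005 | exp(−0.013) = 98.7% | exp(−0.018) = 98.2% | 0.5 points |
| 0.010 | 98.7% | exp(−0.023) = 97.7% | 1.0 point |
| 0.020 | 98.7% | exp(−0.033) = 96.8% | about 2 points |

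**5. The clock.** Let g be the FNAC-to-randomisation gap in months. The protocol sets no limit on it, so g = 1 to 3 is an assumption. Twelve months after FNAC, S = exp(−hd·(12 − g)/12). With hd = 0.013:
- g = 1: 98.8%, about 92% of the events shown by a 12-month curve from randomisation;
- g = 2: 98.9%, about 83%;
- g = 3: 99.0%, about 75%.

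Against 98.7% from randomisation, the absolute shift is 0.1 to 0.3 points.

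For the arm comparison, a null logrank simulation used 88 versus 44 patients, 2,000 runs, a disease hazard of 0.15 per year, censoring uniform over 1 to 5 years and a gap uniform over 0.5 to 4 months. The 0.15 is a further assumption, far above the rate in step 4. Rejection was 5.3% from randomisation and 5.4% from FNAC. The Monte Carlo standard error is √(0.05 × 0.95/2000) = 0.5 points, so the two do not differ.

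**The case against.** The best defence is that little rests on this endpoint. Disease-free survival is one of many secondary endpoints, SO1f calls it short-term, and section 8.8 collects primary and secondary outcomes over one year. Deaths are not hidden: overall survival is reported by arm with death as the event, and section 9.2.2 has fatal events reported expeditiously. A death from thyroid carcinoma with no earlier recorded disease event is unlikely within a year. The event definition may also be left to a statistical analysis plan.

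All of this limits the weight, and most of it stands. It does not make the rule right. Section 10.1 does not leave the handling of death open: it states a rule that conflicts with the endpoint's name. Reporting overall survival separately does not turn the other curve into disease-free survival.

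Four stronger readings might be inferred, and the protocol does not support them.

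- *The arm with more deaths gets the better curve.* Censoring a death does not by itself raise that arm's curve relative to the other. If censoring is independent of disease risk, the net estimate is unaffected. The curve simply omits deaths that its name says it includes.
- *A large share of failures is lost.* Section 13.1.2 quotes, for T1 to T4, "85%, 73%, 60%, 56% (for 10y DFS) and 100%, 93%, 87%, 72% (for 10y OS". Dividing deaths by failures gives 7/27 = 26%, 13/40 = 33% and 28/44 = 64% for T2 to T4. With the size mix of Table 4 (50/37/13%), it gives 4.28/22.69 = 19%. These are 10-year results in confirmed cancer, node-positive according to the title in the reference list. Table 4 describes all enrolled nodules, of which about 74% are expected to be benign. The ratio also presumes that the cited disease-free figures count deaths, which the protocol does not say. Section 13.1.2 itself gives 100% five-year overall survival for stages I and II.
- *The harm falls on the five-year review.* Sections 2.2.1 and 8.8 tie that horizon to false negatives, costs, utilities and general longer-term effects. They do not specify disease-free survival there.
- *The early clock biases the comparison.* The gap arises before randomisation and is balanced by it.

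**Conclusion.** The concern holds as a defect of definition. As written, SO1f would report a net time-to-disease-event curve as disease-free survival. At the short-term horizon the effect is small: 1.1 or 2.3 points for each uncounted death, or 0.5 to 2 points at 12 months under assumed death rates of 0.5 to 2% per year. The primary endpoint, the sample size and the stopping and end-of-study false-negative rules do not depend on it.

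The FNAC origin is a lesser matter. It lifts the absolute curves by about 0.1 to 0.3 points under the assumed gap and disease rate, and leaves the arm comparison essentially as it was.

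**What to change.** In section 10.1, choose one of two wordings:

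- **Keep the name.** Count death from any cause as a disease-free survival event and censor only at last follow-up.
- **Keep the present target.** Rename the endpoint, for example time to recurrence or time to disease event. Treat death as a competing event and report cumulative incidence by arm.

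Either way, define the disease event, identically in both arms. At randomisation no nodule has been removed, so every patient with cancer already has disease. Cancer present and unresected at time zero must not itself be an event. If it were, about 0.258 × 132 = 34 patients would have one by definition, using the pooled prevalence in Appendix IV. The definition must also cover patients with benign histology and those under surveillance.

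As a minor change, start both survival endpoints at randomisation. Every participant has that date. Section 4.2 admits core needle biopsy in place of FNAC, so some may lack the origin now specified.

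The cost is a wording change. Overall survival already needs the date of death and randomisation is central, so no new data collection follows. The change should be dated before survival is examined by arm.

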8.3.3 Questionnaires

All study patients will be asked to fill in 6 self-administered questionnaires in their native language at baseline, after 3 months (or directly after surgery+¹³¹I-RIA), after 6 months and after 12 months. Together these 6 questionnaires take about 30-45 min to fill in:

- RAND-36 V2.0 (SF36-II): The RAND-36 V2.0 is a validated translation in Dutch of the Short Form health survey (SF36-II) comprising 36 questions yielding a 9-scale profile of function health, wellbeing and psychometrically based physical and mental health [57]. It takes approximately 5 minutes to complete. As the SF36-II was not originally designed for use in economic evaluations or to determine QALYs, the SF-6D can be created by applying a scoring method, focusing on seven of the eight health domains of the SF36-II [58] (Appendix VII: , §15.7 p98).
- EQ-5D-5L: EuroQol 5-dimensional 5-level questionnaire: indexing health status, 2 pages including a single visual analogue scale (VAS) [59]. It takes approximately 5 minutes to complete (Appendix VII: , §15.7 p98)..

- iPCQ: Productivity Costs Questionnaire, 12 questions on health and losses of productivity in paid and unpaid labour [60]. It takes approximately 5 minutes to complete (Appendix VII: , §15.7 p98).
- iMCQ: Medical Consumption Questionnaire, indexing direct costs of self-reported health care consumption through 35 short questions. It takes a maximum of 20 minutes to complete [61].
- ThyPRO: Thyroid Patient-Reported Outcome, a disease specific 13-scale 84-item questionnaire designed for benign thyroid disease, but being investigated for use in DTC.
 [62] It takes approximately 14 minutes to complete (Appendix VII: , §15.7 p98).
- DT&PL: Distress Thermometer: a 11-point VAS including a 35-item problem list [63]. Based on expert opinion (by dr. [name], endocrinologist at Radboudumc), we will only use the VAS, since the 35-item problem list mostly overlaps with the content of the other questionnaires. The entire DT&PL takes approximately 5-10 minutes to complete. We estimate that the VAS itself will take a maximum of two minutes to complete. (Appendix VII: , §15.7 p98).

Questionnaires are returned to the PI either by mail or email.

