10.3 Univariate analysis

All comparisons will be made using the general requirements for relating research questions as stated in Table 6, p66.

Characteristics of (independent) study-arms will be compared using either t-tests ((log)normal) or Wilcoxon rank-sum tests for continuous variables (e.g. age, SUV, hospitalisation days, volumes of care used, questionnaire scores). For categorical data either Fisher exact tests or χ^2 tests will be used (e.g. sex, unbeneficial patient management).

With respect to the primary research question, fractions unbeneficial patient management therefore will be compared using Fisher exact tests or χ^2 tests.

Relations between variables will be univariately described by the parameters from Table 7, p66. These parameters are compared using the tests from Table 8, p67.

Scale:	Groups:	Dependency:	Group Size:	Distribution:	Test:
Continuous	1	n/a	n≥30	(Normal)	t-test
(and			n<30	Normal	_
categorical ordinal)				Not normal but transformable	Transform than t-test
				Not normal, not transformable	Sign test
	2	Independent	n≥30	(Normal)	t-test
	-	n<30		Normal, equal variances	
				Normal, non-equal variances, equal n's	-
				Normal, non-equal n's, transformable	Transform than t-test
				Normal, non-equal variances, non-equal n's, not transformable	Wilcoxon rank-sum tes (= Mann-Whitney U test
				Not normal, transformable	Transform than t-test
				Not normal, not transformable	Wilcoxon rank-sum tes (= Mann-Whitney U test
		Dependent	n≥30	(Normal)	Paired t-test
			n<30	Normal	_
				Not normal, transformable	_
				Not normal, not transformable	Wilcoxon signed ranks
	≥3	Independent	n/a	Normal, 1 factor	One-Way ANOVA
				Normal, ≥2 factors	Two-Way or othe ANOVA
	_		Not normal	Kruskal-Wallis for Factor (+Dunn's posthoo test)	
		Dependent	n/a	Normal	Repeaed Measures
				Not normal	Friedman ANOVA
Categorical (Nominal)	1		np≥5 and n(1- p)≥5		z-approximation
	2	Independent	Expected cell frequencies <5		Fisher's Exact Test
≥3	_		Expected cell frequencies ≥5		X ² or z-approximation
		Dependent			McNemar or ĸ
	≥3	Independent	Expected cell frequencies <5		Collapse categories fo X^2
			Expected cell		X ²
			frequencies ≥5		

Table 6: General Requirements for selection of Statistical tests used for univariate analysis (comparison)

Predicting each other	Parameter:
	Relative Risk
	Spearman's ρ squared
yes	Regression
no	Pearson's Correlation R squared (log)normal
	Spearman's p squared (not-normal)
	yes

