10.6 Cost-Effectiveness Analysis (CEA)

General considerations:

This part of the study evaluates the potential efficiency of incorporating FDG-PET/CT in the diagnostic work-up versus usual practice in adult patients with FNAC-indeterminate thyroid nodules from a societal perspective. The economic evaluation is based on the general principles of a cost-effectiveness analysis and is performed alongside the randomised controlled clinical trial. Primary outcome measures for the economic evaluation, considering the 12 months follow-up period, are costs (direct and indirect) and quality adjusted life years (QALY). The incremental cost-effectiveness ratio (ICER) "cost per QALY gained" will be computed and uncertainty will be determined using the bootstrap method or Fieller method. A cost-effectiveness acceptability curve will be derived that is able to evaluate efficiency by using different thresholds (Willingness to Pay) for a QALY. The impact of uncertainty surrounding deterministic parameters (e.g. prices) on the ICER will be explored using one-way sensitivity analysis on the range of extremes. Secondary ICERs such as cost per unbeneficial patient management decrease will be presented and analysed as above. Furthermore, incremental Net Monetary Benefit (iNMB) will be computed based on a Willingness-to-Pay threshold of €80,000/QALY, as stated before.

Cost-analysis:

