The cost-analysis exists of two main parts. First, on patient level, volumes of care will be measured prospectively using questionnaires filled-in by patients, completed by case record forms and patient files (supported by patient-based diaries). Per study-arm (experimental and control) full cost prices will be determined using activity-based costing (obviously) excluding the costs of the FDG-PET/CT in the control study arm. Cost items included are e.g.: surgical costs, costs of ¹³¹I-RIA, admission costs, costs for complications (secondary surgery, ICU etc.), out-patient clinic visits, use of relevant medications (calcium, vitamin D, 69iothyronine69, 69iothyronine etc.), blood tests ((para)thyroid function tests) and additional investigations (US, CT, biopsy, histopathology, etc.). Productivity losses for patients (sick leave) will be estimated using the iPCQ. The friction cost-method will be applied following the Dutch guidelines [68]. Also travel time to an out-patient clinic and related expenses will be considered using the iMCQ. The second part of the cost-analysis consists of determining the cost prices for each volume of consumption in order to use these for multiplying the volumes registered for each participating patient. The Dutch guidelines for cost-analysis will be used [68]. For units of care/resources where no guideline of standard prices is available, real cost prices will be determined.

Patient outcome analysis:

The effect analysis adheres to the design of a randomised controlled trial and measures at baseline (T0) and after surgery+¹³¹I-RIA/2 months, 6 months and 12 months (T1-3) follow-up. To measure the quality of the health status of the patients, a validated HRQoL instrument will be used: the EQ-5D-5L. This HRQoL instrument will be completed by the patients and is available in a validated Dutch translation [70]. The EQ-5D-5L is a generic HRQoL instrument comprising five domains: mobility self-care, usual activities, pain/discomfort and anxiety/depression. The EQ-5D-5L index is obtained by applying predetermined weights to five domains. This index gives a societal-based global quantification of the patients' health status on a scale ranging from 0 (death) to 1 (perfect health). Patients will also be asked to rate their overall HRQoL on a visual analogue scale (EQ-5D-VAS) consisting of a vertical line ranging from 0 (worst imaginable health status) to 100 (best imaginable).

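### The ban on completing missing values makes the 12-month QALY a complete-case outcome, no baseline adjustment is tied to the HRQoL or QALY comparison, and the first follow-up round is dated in two ways

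*Protocol*

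**What the plan says.** Section 10.1 opens by covering all statistical and economic analyses and then sets the rule: "Missing values will not be completed by any means (e.g. average". The fraction missing will be reported. The stated consequence is "Multivariate analysis might therefore only be performed on a subset of patients (without missing values in all independent parameters", with an expectation that this subset exceeds 95% of the study population.

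Section 10.3 compares the arms by "t-tests ((log)normal) or Wilcoxon rank-sum tests for continuous variables (e.g. age, SUV, hospitalisation days, volumes of care used, questionnaire scores".

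Section 10.6 states: "Primary outcome measures for the economic evaluation, considering the 12 months follow-up period, are costs (direct and indirect) and quality adjusted life years (QALY". Uncertainty is to come from the bootstrap or the Fieller method. No covariate is named.

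Section 8.3.3 has six self-administered questionnaires completed "at baseline, after 3 months (or directly after surgery+¹³¹I-RIA), after 6 months and after 12 months". Section 10.6 says that the effect analysis "measures at baseline (T0) and after surgery" plus radioiodine ablation or 2 months, then at 6 and 12 months.

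**The concern.** The rule is explicit, so it is not a gap that a statistical analysis plan could simply fill: a plan that imputed EQ-5D-5L scores would contradict the protocol. The reassurance of more than 95% is limited to independent parameters in multivariate models. It does not speak to four rounds of questionnaires returned by mail or email.

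Non-response may also be selective. Only PET-negative patients in the experimental arm, about 32 of 132 (section 3), learn their allocation, because their surgery is cancelled. Section 1.4.3 names the utility of surveillance after a negative scan as the most influential parameter of the 5-year model, whose net benefit falls to zero at a utility of 0.953. The trial's evidence on that quantity comes from this small group.

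The baseline score, collected in every patient, is given no role in the arm comparison of scores or QALYs. HRQoL is not a minimisation factor either (section 8.2.2).

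**Working it through.** **The plan's own loss figure.** Section 4.4 allows 15% data loss at the final endpoint: 111 / 0.85 = 130.6, rounded up at 2:1 to 88 + 44 = 132. This is one overall loss. Applied once to the QALY it leaves 0.85 × 132 ≈ 112 patients.

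**Completeness over four rounds.** The protocol states no non-response rate per round, so m is an assumption. If rounds are missed independently, the share complete is (1 − m)⁴:

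| m per round | share complete | of 132 |
|---|---|---|
| 3% | 0.97⁴ = 0.885 | 117 |
| 5% | 0.95⁴ = 0.815 | 108 |
| 10% | 0.90⁴ = 0.656 | 87 |
| 15% | 0.85⁴ = 0.522 | 69 |

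If the same patients miss every round, the share is simply 1 − m. For 95% of patients to have all four rounds under independence, m would have to be 1 − 0.95^(1/4) ≈ 1.3%. Among the 32 or so PET-negative experimental patients, 52% to 85% completeness means about 17 to 27 with a QALY.

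**Gain from baseline adjustment.** Residual variance is multiplied by 1 − r², where r is the correlation of baseline with outcome (assumed). At r = 0.5 the factor is 0.75, a cut of 25%. At r = 0.7 it is 0.51, a cut of 49%.

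**Size of a chance baseline difference.** The standard error is SD × √(1/88 + 1/44) = SD × 0.1846. For an assumed utility SD of 0.10, 0.20 and 0.25 this gives 0.018, 0.037 and 0.046. To express one standard error as net benefit, multiply by r (taken as the slope of QALY on baseline utility, which assumes equal SDs) and by €80,000 per QALY (section 10.6):

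- SD 0.10, r = 0.5: 0.01846 × 0.5 × 80,000 ≈ €740
- SD 0.25, r = 0.7: 0.04616 × 0.7 × 80,000 ≈ €2,585

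**First follow-up round.** Under the usual trapezium rule (an assumption; the protocol does not name one), each round is weighted by half the sum of its adjacent intervals, divided by 12 months. Rounds at 0, 3, 6 and 12 months get weights 0.125, 0.25, 0.375 and 0.25. Rounds at 0, 2, 6 and 12 months get 0.083, 0.25, 0.417 and 0.25. The two sections therefore imply different QALYs from the same answers. The round also follows treatment in operated patients and the calendar in the others, so nominal times fit the two groups differently.

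**The case against.** Several stronger readings are tempting, and the document does not support them.

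- **That the rule breaks intention to treat.** The plan says "All analysis will be performed according to the intention to treat", but sections 4.4 and 8.5 define this as analysis by allocated arm. Leaving values missing does not contradict that definition.
- **That incomplete patients leave every comparison.** A test of one round can use whoever answered it, and a mixed model fills in nothing. Section 10.6 completes volumes of care from case record forms and patient files, so costs do not rest on four questionnaires.
- **That about half the QALYs will be lost.** The 52% needs 15% non-response at each round, whereas the protocol's 15% is a single overall loss.
- **That the plan rules out using baseline.** Section 8.1.2 asks for the temporal relation of scores, Table 6 lists repeated measures and Table 10 lists ANCOVA. A separate analysis plan could adopt adjustment without contradicting the protocol.
- **That chance imbalance biases the net monetary benefit.** Under randomisation it is sampling variation, which the bootstrap or Fieller interval already reflects. Adjustment buys precision.
- **That such an imbalance matches the whole expected gain.** The 0.036 QALY in section 1.4.3 is a 5-year model figure, and the trial measures 12 months.

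All of this narrows the point, but the core remains. A patient-level 12-month QALY cannot be computed directly when a round is missing and completion is forbidden. Repeated measures and ANCOVA are listed generically and never assigned to the HRQoL or QALY comparison; section 10.4 also admits candidate variables only after a significant univariate association, which is not a prespecified adjustment. The timing contradiction stands on the text alone.

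**Conclusion.** The point holds in limited form. Followed as written, section 10.1 makes the 12-month QALY complete-case. About 85% of patients would have one if the single 15% loss applies, and 89% to 52% under assumed independent non-response of 3% to 15% per round. Whether the loss would be selective cannot be known from the protocol; it is plausible because unblinding is confined to one subgroup of one arm.

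The missing baseline adjustment is a loss of precision worth 25% to 49% of residual variance at r = 0.5 to 0.7. One standard error of chance baseline difference corresponds to roughly €740 to €2,585 of net benefit per patient. Both figures rest on an SD and a correlation that the protocol does not give.

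The first follow-up round is inconsistently defined. The affected outcomes are the HRQoL and economic ones, with costs affected least. The primary endpoint, unbeneficial treatment, is not touched.

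**What to change.** **Section 10.1.** Limit the ban so that it does not apply to HRQoL scores, EQ-5D-5L and QALYs, or cost items still missing after file review. For these, specify either multiple imputation or a mixed model, with complete cases as a sensitivity analysis. The imputation should be run by arm or include arm in the model, and use baseline and other-round scores, age, sex, nodule size, Bethesda class and PET result. Leave out histology, which is absent by design when surgery is cancelled, and individual centre, since several of the 15 sites have five or fewer patients (Table 3).

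**Sections 10.3 and 10.6.** Adjust HRQoL scores for the baseline score and QALYs for baseline EQ-5D-5L utility, named in advance.

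**Sections 8.3.3 and 10.6.** Reconcile the definition of the first follow-up round, and compute QALY areas from actual completion dates.

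The cost is protocol or analysis-plan wording and some analysis time; no new data are needed. The drawback is reliance on a missing-at-random assumption, which the complete-case comparison can probe but not prove.
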